Several subjective outcome measures will be utilized throughout the study. Function specific subjective outcome measures include: Lower Extremity Functional Scale (LEFS), Knee Injury and Osteoarthritis Outcome Score for patellofemoral pain and osteoarthritis (KOOS-PF), the Tenger Activity Scale, and the Single Assessment Numerical Evaluation (SANE). Pain levels will also be assessed utilizing the Numerical Rating Scale (NRS) Pain Scale, 1-10. The LEFS is a validated 20-question PROM survey used for the measurement of lower extremity function based on the patients' initial function, ongoing progress, and long-term outcome. The KOOS-PF is an 11-question survey that is used to assess five outcomes; they include knee related quality of life, activities of daily living, sport and recreation function, activities, and pain and symptoms. The SANE is a single-item question used globally to assess function. The Numeric Rating Scale is one question pain intensity scale that assesses pain level on a 1-10 scale. The Fear Avoidance Beliefs Questionnaire (FABQ) is a 16 question likert scale questionnaire aimed at assessing how everyday activities assess the patient's current level of pain. The Tenger Activity Scale determines the level of activity prior and post injury. It will be collected at evaluation, 6 months and 12 months. The dynamometry, LEFS, SANE, NRS and KOOS-PF are documented during the initial evaluation, 4-week, and 9-week or at the end of PT. The PROs will be completed at evaluation, 4-week, 9-week or at the end of PT, as well as with a 6 month and 12 month follow-up. See attachment for chart.

Activity	Enrollment	Baseline	4-week	9-week or end of PT	6 months	12 months
Assessed for eligibility			X			
Demographics/baseline activity level			X			
Randomization			X			
Group allocation			X			
PT session			X			
Intervention Group only BFR w/PT	X		X	X		X
Control Group sham BFR w/PT	X		X	X		X
PROs	X	X	X	X	X	X

Subject identification, recruitment, and pre-assessments:

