Consented subjects will be assigned to either the sham-comparator control group or BFR Intervention Group according to a pre-generated randomized assignment sheet. Each randomized assignment sheet will consist of equal control and equal BFR assignments whose order has been randomized using the random list generator at <https://www.random.org/lists/>. We will use blocked randomization to reduce the risk that patients will be assigned to the BFR treatment and sham control groups at unequal frequencies. These blocks will have a size of 6. Co-Investigators at each site will be given a unique list with a number of assignments that is in proportion to the number of subjects expected to be recruited at the site; additional assignment lists will be generated if needed. These co-Investigators will be responsible for communicating group assignments to study therapists delivering the intervention, and for ensuring that randomization and treatment order is maintained. It is expected that if the assignment scheme is not maintained for whatever reason, that they will report the incident to the PI and how it was/or still needs to be rectified. No matter group assignment, all consented subjects will be asked to conduct all assessments. Utilizing a proposed sample size of 96 participants, the study will continue until there are at least 40 participants who complete all study related activities in both the intervention and control groups.

Study protocol:

After being identified as a potential study participant and being consented, participants will be randomly assigned to the sham control or BFR group. All physical therapy sessions will consist of typical, standard

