1.2 Data collection and analysis

Along with their standard therapy session reassessments (including routine session notes and progress notes), participants will be asked to complete the PROs at 4-week, 9-week or at the end of PT sessions, 6-month and 12-month intervals. The PROs will be completed by paper and pen while at a therapy session. Baseline, 4-week, and 9-week or end of PT sessions assessments will be completed as part of the routine PT session evaluation process. If the participant is not coming in to Gaylord for appointments, the 6 and 12-month assessments will be completed by phone with the participant or paper copies will be mailed to their last known address. If necessary, an email will be sent to remind them of the study and scheduled assessments.

Information regarding the security of participant's data will be shared with them in the consent form as well as upon request. All information collected specifically for the study will be stored on password protected computers in locked offices. The paper copies of the assessment forms completed as part of routine PT sessions will be stored according to Gaylord procedures in the hard copy of the patient's medical record. Information from the forms will be pulled by study staff and shared across sites only after it is de-identified.

After data is collected and de-identified, it will be analyzed using GraphPad Prism version 9.3.1, or other appropriate statistical software as necessary. Adjustments for abnormal distribution and unequal variance will be applied as necessary. To compare pre- and post-intervention measurements over time on subjective and objective outcome measures, we will use a two-way repeated measures analysis of variance or independent samples t-test to determine the effect of treatment groups (BFR + standard of care therapy and sham + standard therapy). For relationships between variables, we will use correlation and regression analyses as necessary. For categorical data, we will use chi-square testing or Fischer's exact test as necessary. Exact analysis for each test will depend on variance and distribution/normality of data set. We will perform an interim analysis at 50 % participant recruitment in order to assess the effects of the BFR therapy and safety for the subjects, and potential for change in sample size. We will not preclude the possibility of conducting other post-hoc data analyses as appropriate and approved by the IRB.

References

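### No remote route is stated for the 4-week and 9-week PROs, so participants who stop attending therapy early may have these outcomes missing, possibly not at random

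*Combined protocol and SAP*

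**What the plan says.** Section 1.2 (Data collection and analysis) sets the default: "The PROs will be completed by paper and pen while at a therapy session". It then fixes the setting of the early visits: "Baseline, 4-week, and 9-week or end of PT sessions assessments will be completed as part of the routine PT session evaluation process". The provision for people who are not attending follows, and it names only the two late visits: "If the participant is not coming in to Gaylord for appointments, the 6 and 12-month assessments will be completed by phone with the participant or" by mailed form. The next sentence adds contact but no means of collection: "If necessary, an email will be sent to remind them of the study and scheduled assessments".

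Section 1.1 states a wider intention. Under Subject assignment: "No matter group assignment, all consented subjects will be asked to conduct all assessments". Under Equipment and Instruments, the schedule lets a final therapy visit stand in for week 9: "The PROs will be completed at evaluation, 4-week, 9-week or at the end of PT, as well as with a 6 month and 12 month" assessment. Neither place says how PROs are obtained from someone who has stopped therapy.

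**The concern.** The Exercise Protocol covers weeks 1-4 and 5-8, so the 4-week and 9-week PROs are the measures taken during and just after treatment. Collecting them only at a therapy session makes observing the outcome depend on continued attendance. Attendance could plausibly differ by arm, because one arm trains with the cuff inflated to 40-80% occlusion and the other with a non-inflated cuff. It could also depend on how the knee is doing, in either direction.

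If so, the early comparison would be between those who kept attending rather than between the randomised groups. The analysis text names a two-way repeated measures ANOVA or a two-sample t-test and no method for missing data. In its standard form the repeated measures ANOVA uses only participants with every time point. Someone with a missing 4-week PRO could then be excluded even though the 6- and 12-month PROs were collected by phone.

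**Working it through.** **Step 1. Routes by visit (section 1.2).**

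| PRO assessment | Stated setting | Stated route if not attending |
|---|---|---|
| 4-week | Routine PT session | None |
| 9-week or end of PT | Routine PT session | None |
| 6-month | Therapy session, if attending | Phone or mailed form |
| 12-month | Therapy session, if attending | Phone or mailed form |

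**Step 2. Who is affected.**
- Stops before week 4 with no further visit: no stated route for either early PRO.
- Stops before week 4 with a discharge visit: the end-of-PT assessment is obtained, but nothing is stated for week 4.
- Stops between weeks 4 and 9 without a discharge visit: no stated route for the 9-week PRO.
- Discharged between weeks 4 and 9 with an assessment: covered by the end-of-PT alternative.

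**Step 3. Yardstick.** The plan gives no figure for early non-attendance. Its only relevant figure is the standardised effect of 0.635 (section 1.1, Sample size; two-tailed alpha 0.05, power 0.80). That reproduces the stated 80: n per arm = 2 × (1.960 + 0.842)² / 0.635² = 38.9, so 39 per arm (78 in total) by the normal approximation. The exact t calculation gives 39.9, so 40 per arm (80 in total). The value 0.635 can therefore be read in SD units.

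**Step 4. Illustrative bias.** Let m be the fraction missing in an arm and g the attender mean minus the non-attender mean, in SD. The observed mean in that arm is off by m × g, so

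bias in the arm difference = m(BFR) × g(BFR) − m(sham) × g(sham).

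All values of m and g below are assumptions; none comes from the documents.

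Same gap in both arms, so bias = (difference in m) × g:
- 25% v 15%: 0.10 × 0.5 = 0.05 SD; 0.10 × 1.0 = 0.10 SD.
- 30% v 10%: 0.20 × 0.5 = 0.10 SD; 0.20 × 1.0 = 0.20 SD.
- Relative to 0.635: 0.05 is 8%, 0.10 is 16%, 0.20 is 31%.

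Equal missingness of 20% in each arm:
- Same gap in both arms: bias 0.
- Gap of 0.5 to 1.0 SD in one arm only: 0.20 × 0.5 = 0.10 SD to 0.20 × 1.0 = 0.20 SD.
- Opposite gaps of 0.5 to 1.0 SD: (0.20 + 0.20) × 0.5 = 0.20 SD to 0.40 × 1.0 = 0.40 SD.

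**Step 5. What such a bias would do to a test.** Take 96 × 0.80 / 2 = 38.4 per arm, so SE = √(2/38.4) = 0.228 SD. With no true effect and bias b, two-sided type I error = Φ(−1.96 + b/SE) + Φ(−1.96 − b/SE). This gives 5.6% for b = 0.05, 7.2% for b = 0.10 and 14% for b = 0.20.

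**The case against.** The strongest reply is that section 1.2 describes the usual setting of each visit and forbids nothing. It does not say that remote collection is confined to the late visits, the reminder email is not expressly limited to them, and section 1.1 wants all assessments from everyone. That is fair: a reader might infer a prohibition, and the text does not contain one. What stands is that a route for non-attenders is written down for two visits and not for the other two, and an email reminder does not collect a questionnaire. Staff following the text as written would have no procedure for the early PROs.

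Other stronger readings are also unsupported:
- *The early outcomes will go missing selectively.* The documents give no dropout reasons or rates by arm. The Exercise Protocol lets the participant decide when a set ends, which may limit any difference in tolerance. Selective loss is a risk, not a finding.
- *Everyone who recovers early is lost.* Those formally discharged before week 9 have the end-of-PT assessment. The recovery mechanism applies to people who simply stop coming, or who leave before week 4.
- *The planned 20% attrition measures the problem.* That figure concerns complete data sets over about a year and can include losses at 6 and 12 months. It is not an early non-attendance rate.
- *Equal dropout would remove the bias.* Only if the gap between attenders and non-attenders is also the same in both arms (Step 4).
- *Remote PROs would protect the target of 40 completers per arm.* Dynamometry at 4 weeks and at 9 weeks or discharge still needs a visit. Someone who quits early would, on a plain reading, still not have completed all activities.

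**Conclusion.** The point holds as a gap in outcome collection that is cheap to close. After an unplanned stop of therapy, the plan states no way to obtain the 4-week PRO, or the 9-week PRO where there was no discharge visit. These values may be missing not at random, and the planned ANOVA in its standard form could lose the participant's later data as well.

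The size is unknown. The range of 0.05 to 0.20 SD rests wholly on assumed differences in non-attendance of 10 to 20 percentage points and an assumed gap of 0.5 to 1.0 SD common to both arms. The bias could be zero, or larger if the gaps run in opposite directions, and its sign cannot be predicted. The figures also do not show how much the fix would recover, since some who quit may decline a call.

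**What to change.** Replace the sentence in section 1.2 on non-attenders with wording such as: *When a participant is not attending Gaylord at the time any PRO assessment falls due (4-week, 9-week, 6-month or 12-month), the PROs will be obtained by phone or by mailed paper copy.* Add that stopping therapy does not end PRO collection, and record the date and mode of each completion. Dynamometry stays visit-only.

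The cost is one changed sentence, two short additions and a few extra calls or mailings, using a procedure already planned for 6 and 12 months. The downside is that some early PROs will be collected by a different mode from the rest, a mix the plan already accepts at the later visits. The change reduces avoidable missing data; it does not supply a method for handling what is still missing.

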1.1 Study design

This study will be a multisite, randomized, sham-comparator controlled clinical trial conducted by Gaylord Specialty Healthcare Physical Therapy, (GSHPT) in Wallingford, Cheshire, Cromwell, Madison, CT, and the University Of Connecticut Health Center (UCHC) in Farmington, CT. All physical therapy related sessions will be conducted at the GSHPT locations listed above. Due to the nature of the intervention, participants and investigators will not be able to be masked to the intervention.

Participants may not know they are in the intervention or sham group and therapists will not confirm or deny their placement. The assessor will not be able to be masked to group assignments, as the presence or absence of certain variables in the dataset, namely the use of BFR inflation, will immediately reveal group assignment.

Sample size:

An *a priori* power analysis for a two-tailed t-test was performed for sample size estimation. With an alpha = .05, power = 0.80, and effect size of 0.635, the projected sample size needed for complete data sets is approximately N = 80. Thus, our proposed sample size of N = 96 will be more than adequate for the main objective of this study, and should also allow for an expected attrition rate of 20%.

Recruitment for this study will remain open until the target N of 80 complete datasets have been collected. This power analysis was performed using data from Dolak's¹ study on PFPS conducted in 2011. Sample size and protocol was also influenced by Brightwell's study on BFR after patellar instability².

Study Timeline:

Participants will be enrolled in the study for approximately 1 year. Starting with their evaluation and consent at the beginning of their therapy sessions, they will complete prescribed therapy and continue to complete PROs within 4-week, 9-week, 6-month and 12-month intervals. We anticipate the study will take approximately 3 years to complete.

Participants and Settings:

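### The plan sets no analysis set or missing-data method for outcomes repeated over up to five visits; a complete-data ANOVA or a 12-month t-test would compare only those who stayed

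*Combined protocol and SAP*

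**What the plan says.** Section 1.2 (Data collection and analysis) gives the between-arm analysis: "To compare pre- and post-intervention measurements over time on subjective and objective outcome measures, we will use a two-way repeated measures analysis of variance". The same sentence then offers an independent samples t-test as an alternative, and a later sentence makes the exact analysis depend on the variance and distribution found in the data. Non-normality and unequal variance are provided for; missing values are not mentioned.

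Patient-reported outcomes are due at baseline, 4 weeks, 9 weeks or end of therapy, 6 months and 12 months (1.1, Equipment and Instruments; 1.2). Dynamometry has three time points and stops at 9 weeks or discharge.

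Section 1.1 counts participants as completers throughout. Under Sample size, "the projected sample size needed for complete data sets is approximately N = 80", and "Recruitment for this study will remain open until the target N of 80 complete datasets have been collected". Under Subject assignment, the study continues until there are "at least 40 participants who complete all study related activities in both the intervention and control groups". The enrolment target is 96, with 20% attrition expected. No section defines an analysis set, a missing-data method or a mixed model.

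**The concern.** A classical two-way repeated measures ANOVA works on a full participant-by-visit table. Incomplete records must be dropped, filled in, or handled by a different model, and the plan does not say which. The completer-based sizing and stopping rules make dropping them the natural default.

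Two things are at stake. The first is waste: a participant who gave baseline, 4-week and 9-week scores but missed month 12 would be lost from the analysis of that outcome. The second is selection: the arms are comparable as randomised, but those who stay need not be. One arm trains under 40 to 80% occlusion and the other wears a non-inflated cuff, and the plan says masking is not possible. Reasons for leaving could therefore differ by arm, although the documents give no drop-out rate or reason by arm.

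**Working it through.** **1. The plan's own sample size.** Inputs (1.1, Sample size): "power analysis for a two-tailed t-test was performed for sample size estimation"; "With an alpha = .05, power = 0.80, and effect size of 0.635".
- Normal approximation: n per arm = 2(1.960 + 0.842)² / 0.635² = 38.9, so 39 per arm, 78 in total.
- Noncentral t, with noncentrality d√(n/2): n = 39.91, so 40 per arm. The stated 80 is reproduced.
- Power: 38 per arm (0.635 × √19 = 2.77) 78.0%; 40 per arm (0.635 × √20 = 2.84) 80.1%; 48 per arm (0.635 × √24 = 3.11) 86.8%.

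**2. Participants with partial records.**
- 96 × 0.8 = 76.8 complete, so about 19 of 96 are incomplete.
- 80 complete datasets at 20% attrition need 80 / 0.8 = 100 randomised, so about 20 are incomplete.
- If losses fall after week 9, all 96 have a 9-week value. Using them gives up to 86.8% power at 9 weeks, against 80.1% for 80 completers.

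**3. Scattered missed visits.** Assume each of the four post-baseline visits is missed independently with probability m. The complete fraction is (1 − m)⁴, and the share of collected post-baseline values discarded is 1 − (1 − m)³.

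| m (assumed) | Complete | Of 96 | Values discarded |
|---|---|---|---|
| 5% | 81.5% | 78 | 14% |
| 10% | 65.6% | 63 | 27% |
| 15% | 52.2% | 50 | 39% |

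**4. Selection bias at 12 months.** The documents give no SD, visit correlation or drop-out mechanism. Assumptions: SD 1, higher score better, equal correlation ρ = 0.5 to 0.7 between visits, no true effect. About 20% per arm leave after week 9, with log-odds of leaving falling by 1 per SD of the 9-week score z where drop-out depends on response.
- Mean 9-week score of stayers in that arm: E[z | stay] = E[p(1 − p)] / (1 − 0.20) = 0.139 / 0.80 = 0.173 SD, where p is the probability of leaving given z.
- At 12 months this carries over as ρ × 0.173.
  - One arm only: 0.5 × 0.173 = 0.087 to 0.7 × 0.173 = 0.121 SD.
  - Opposite relations in the two arms (twice that): 0.173 to 0.243 SD.
- The standard error with about 38.4 per arm is √(2 / 38.4) = 0.228. The shifts are then 0.38 and 0.53 standard errors (rejection about 7% and 8%) for one arm, and 0.76 and 1.07 (about 12% and 19%) for opposite relations.
- Simulated trials of 96 agree to within about 0.02 SD: 0.09 to 0.13 SD with 6% to 9% false positives (one arm), and 0.18 to 0.26 SD with 12% to 20% (opposite relations).
- A likelihood estimate using the earlier visits stays within about 0.01 SD of zero on the same data.

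**5. Where there is little or no bias.**
- Same relation in both arms, no true effect: none (rejection 4% to 5%).
- Same relation in both arms, true difference 0.635: completers average 0.58 to 0.60, a shift of about −0.04 to −0.06 SD.
- Drop-out unrelated to response: none.
- A 9-week comparison that uses every 9-week value: none in the step 4 scenario, because everyone still has that value.

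**The case against.** The strongest reply is that the documents never say participants with a missed visit are excluded. Complete datasets appear only in the sizing and recruitment rules, and how the named software treats incomplete records cannot be checked from the documents. That stands: complete-case analysis is an inference from the method, the completer rules and the silence on missing data.

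Second, the plan also allows a t-test, the test it was sized on. A t-test at one visit uses everyone with that visit's values, so at 9 weeks it avoids the loss from later drop-out. That also stands. It does not help at 12 months, where the t-test sees only those still present and carries the step 4 bias.

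Third, a reader might infer that power falls to 78% because 96 less 20% leaves about 77. The documents do not support this, since recruitment stays open until 80 datasets are complete and power there is 80.1%. The rule repairs the count; it leaves selection untouched and partial records unused.

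Fourth, the bias is conditional. It needs drop-out that follows response differently by arm, and the mechanism here is assumed. The near-zero likelihood result depends on drop-out being driven by a recorded score. Phone, mail and email follow-up at 6 and 12 months may also keep losses below 20%.

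**Conclusion.** The point holds as a gap in the plan that should be closed before analysis. The between-arm method is left as a choice between two tests, with no analysis set and no handling of missing values. Either test, in the form the completer rules suggest, would rest the 12-month comparison on those who stayed. Under the assumptions in step 4 the bias is about 0.09 to 0.13 SD if response-related drop-out occurs in one arm only, and about 0.18 to 0.26 SD if the arms lose people for opposite reasons. The sizing effect is 0.635 SD.

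Three stronger readings go too far. The documents do not establish that a participant who misses one visit contributes nothing. Drop-out that follows response does not always bias the comparison; with no true effect and the same relation in both arms it does not. A 9-week bias from later drop-out arises only if the 9-week comparison is limited to participants who went on to complete, which no section requires. Dynamometry is less affected, because a missed 6- or 12-month visit removes nobody from it.

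**What to change.** In 1.2, replace the choice between repeated measures ANOVA and t-test, for between-arm comparison of repeated outcomes, with one pre-specified likelihood-based mixed model for repeated measures. It should have arm, visit as a category, arm-by-visit terms, the baseline score and an unstructured covariance. Fit it to all randomised participants with any follow-up value, analysed as randomised, without dropping incomplete records. Replacing the ANOVA alone would not be enough, since the t-test and the data-dependent choice would remain.

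Keep the complete-dataset comparison as a secondary analysis. Add a sensitivity analysis for drop-out that depends on unrecorded values, which the complete-dataset comparison does not probe.

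The cost is revised wording and slightly more analysis work, in software that 1.2 already permits, with no new data. The model assumes that drop-out is explained by recorded values. This cannot be verified from the data, but it is weaker than the assumption complete-case analysis needs.

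### The repeated measures ANOVA does not name its treatment test; read literally, that test averages in baseline, and the stated 80% power is shown only for a t-test

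*Combined protocol and SAP*

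**What the plan says.** Section 1.1 (Sample size) states: "An *a priori* power analysis for a two-tailed t-test was performed for sample size estimation". The inputs follow: "With an alpha = .05, power = 0.80, and effect size of 0.635", leading to about 80 complete datasets. The section names no outcome or visit, and does not say whether the effect size refers to a follow-up value or a change. Allocation is equal ("Each randomized assignment sheet will consist of equal control and equal BFR assignments"), and the study continues until there are "at least 40 participants who complete all study related activities in both the intervention and control groups".

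Section 1.2 describes a comparison of values from before and after the intervention, across time, and continues: "we will use a two-way repeated measures analysis of variance or independent samples t-test to determine the effect of treatment groups". It then leaves the exact analysis to depend on the variance and distribution of the data. No section names a group-by-visit term, a primary visit, a primary outcome or a baseline-adjusted analysis.

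Strength by dynamometry is measured at three visits: initial evaluation, 4 weeks, and 9 weeks or discharge (section 1.1, Equipment and Instruments). The questionnaires are collected at five: baseline, 4 weeks, 9 weeks or end of therapy, 6 months and 12 months (section 1.2).

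**The concern.** In a two-way group-by-visit ANOVA, the term that matches the plan's words is the group main effect. It is the between-arm difference averaged over every visit in the model. If baseline is one of those visits, it adds a difference whose expected value is zero under randomisation, and the average is pulled toward zero. The reported effect would then be smaller than the follow-up difference that clinicians want to know, whatever the correlation between visits.

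Power is a separate matter. The trial was sized for a t-test, while the first analysis named is an ANOVA whose test term is left open. Depending on the term and the number of visits, power at the planned size can be well below or well above 80%, and nothing in the plan says which applies.

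**Working it through.** **Inputs from the documents.** Two-sided alpha 0.05, power 0.80 and effect size d = 0.635 (section 1.1, Sample size); 1:1 allocation and n = 40 completers per arm (section 1.1, Subject assignment); three dynamometry visits and five questionnaire visits, each count including baseline.

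**Assumptions not in the documents.** No expected baseline difference; equal SDs at all visits (set to 1); the same effect d at every follow-up visit; a common between-visit correlation r, run at 0.3, 0.5 and 0.7.

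**Step 1: the plan's own figure.** Two-sample t-test, noncentrality d × √(n/2) = 0.635 × √20 = 2.84 on 78 df. Power is 80.1%. Solving for 80% gives 39.9 per arm, so 40 per arm and 80 in total. The stated size reproduces.

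**Step 2: dilution of the group main effect.** With T visits, of which k = T − 1 are follow-up visits, the expected group effect is d × k/T.
- Three visits: 0.635 × 2/3 = 0.42 SD.
- Five visits: 0.635 × 4/5 = 0.51 SD.

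This does not depend on r.

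**Step 3: power of the group main effect.** A patient's mean over T visits has variance (1 + (T − 1)r)/T. The standardised effect is d(k/T) / √[(1 + (T − 1)r)/T]. At r = 0.5:
- Three visits: 0.423/√0.667 = 0.518, power 63%.
- Five visits: 0.508/√0.600 = 0.656, power 83%.

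**Step 4: omnibus group-by-visit F test.** Noncentrality is (n/2) × d² × (k/T)/(1 − r), with k and 78k df. At r = 0.5:
- Three visits: 20 × 0.403 × 0.667/0.5 = 10.75, power 84%.
- Five visits: 20 × 0.403 × 0.8/0.5 = 12.90, power 83%.

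**Step 5: follow-up values only.** The mean of k follow-up visits has variance (1 + (k − 1)r)/k. With one follow-up visit and baseline as covariate, the residual variance is 1 − r². At r = 0.5 that gives 0.635/√0.75 = 0.733 and power 90% (the one df spent on the covariate is ignored).

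**Results, power at 40 per arm:**

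| Test | r = 0.3 | r = 0.5 | r = 0.7 |
|---|---|---|---|
| t-test, one follow-up visit | 80% | 80% | 80% |
| Group main effect, 3 visits | 73% | 63% | 55% |
| Group main effect, 5 visits | 92% | 83% | 73% |
| Omnibus group-by-visit, 3 visits | 69% | 84% | 97% |
| Omnibus group-by-visit, 5 visits | 67% | 83% | 97% |
| Mean of 2 follow-up visits, unadjusted | 94% | 90% | 86% |
| Mean of 4 follow-up visits, unadjusted | 98% | 94% | 89% |
| One follow-up visit, baseline as covariate | 84% | 90% | 98% |

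For 80% power, the main effect would need 48/60/72 per arm with three visits and 28/38/48 with five. It drops below 80% from a correlation of about 0.2 with three visits (78% at 0.2) and from about 0.6 with five (78% at 0.6). With the same visits and correlation, the mean of the follow-up visits has more power than the main effect in every cell.

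**The case against.** The best defence is that the plan never names the main effect. The sentence in section 1.2 opens with a comparison across time of values before and after treatment, which fits the group-by-visit interaction equally well, and that term is not diluted in this way. The same sentence offers an independent samples t-test, the test for which the 80% was calculated, and that figure is correct. With five visits even the main effect keeps 80% power up to a correlation of about 0.5, because averaging more visits also reduces variance. All of this stands.

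It rules out three stronger readings. A reader might infer that the plan has chosen a diluted test; the text only permits that choice. A reader might infer that the 80% power is wrong; it holds for one of the two named options and for some versions of the other. A reader might work out power for one visit before and one after treatment, where the main effect has only 41/37/33%; but no outcome is scheduled at just two visits.

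The defence does not settle the point. The ANOVA is named first, the choice between the two tests is left to the data, and no other section fixes a term or visit. Reading the plan as the interaction does not secure 80% either: at correlation 0.3 the omnibus test has 69% (three visits) or 67% (five), less than the 73% and 92% of the main effect.

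**Conclusion.** The point holds as one of an unnamed test with a real consequence. If the ANOVA group effect is used with baseline among the responses, a constant follow-up effect is reported at 2/3 of its size for dynamometry or 4/5 for the questionnaires. That is algebra, and needs only randomisation and a constant effect.

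The consequence for power is conditional. The stated 80% is sound for a two-sample t-test at 40 per arm and is not assured for the ANOVA: across correlations of 0.3 to 0.7, main-effect power runs from 73% down to 55% with three visits and from 92% down to 73% with five. These figures rest on assumed correlations, equal SDs and an effect that is the same from 4 weeks onward. The documents support none of these directly, so the figures show a range and do not predict the trial's power. The plan should be changed because a follow-up-only comparison avoids the dilution and, under these assumptions, has more power throughout than the main effect on the same visits.

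**What to change.** In section 1.2, replace the open choice of test with a statement along these lines: *The treatment effect is the between-arm difference at [named follow-up visit], or in the mean of the follow-up visits, estimated from a model whose responses are follow-up values only, with the baseline value of the same measure as a covariate. Neither the group main effect over visits that include baseline nor the omnibus group-by-visit test is used as the test of treatment.* The sponsor should choose between the single visit and the mean, and name the outcome, before the interim analysis at 50% recruitment. If the effect is expected to build up or fade, a single named visit is easier to interpret than a mean.

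In section 1.1 (Sample size), add that the 80% refers to an unadjusted two-sample t-test at one follow-up visit with 40 completers per arm. It may be added that, under the assumptions above, baseline adjustment raises this to about 84/90/98% at correlations of 0.3/0.5/0.7.

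The cost is a few sentences. Baseline values are already collected, so no new data, visits or participants are needed. The price is a commitment: the visit and the test can no longer be chosen after the data are seen.
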